3.3.2 Inclusion criteria

1. Diagnosis of T2DM prior to informed consent.

Note: Documentation should be available before randomization at latest. Confirmation can be in the form of formal documents or by verbal communication of the date of diagnosis from a patient or from their primary care physician (if records are not available). It is up to the medical judgment of the Investigator to deem if the information is accurate.

2. Male and female black/African American patients on diet and exercise regimen who are EITHER

drug-naïve (defined as absence of any oral antidiabetic therapy, glucagon like peptide-1 (GLP-1) analog or insulin for 12 weeks, 16 weeks for pioglitazone prior to randomisation)

OR

pre-treated with stable dose of

- Metformin only, or
- Sulfonylurea only, or
- DPP-4 inhibitor only, or
- metformin plus sulfonylurea, or

Proprietary confidential information.

© 2016 Boehringer Ingelheim International GmbH or one or more of its affiliated companies. All rights reserved.

This document may not - in full or in part - be passed on, reproduced, published or otherwise used without prior written permission.

- metformin plus DPP-4 inhibitor.

Treatment has to be unchanged for a minimum of 12 weeks prior to randomization.

Dose for metformin: maximum tolerated dose

The maximum daily dose of SU or DPP-4 inhibitor should not exceed that stated in the local label.

3. HbA1c of $\geq 7.0\%$ (53 mmol/mol) and $\leq 11.0\%$ (97 mmol/mol) at Visit 1 (screening).
4. Mean seated SBP 140-180 mmHg at Visit 1 (screening).
5. Successful completion of baseline ABPM testing with a mean SBP 135-175 mmHg prior to randomisation.
6. Treatment with stable doses of at least one but not more than 4 antihypertensive medication ≥ 4 weeks prior to randomisation.
7. Age ≥ 18 years at Visit 1 (screening)
8. Signed and dated written informed consent by date of Visit 1 in accordance with Good Clinical Practice (GCP) and local legislation

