3.3.5 Re-screening

Re-screening is permitted for the following categories of screen failed patients only:

- Patients who were screen failed due to exclusionary background anti-diabetic therapies (sulfonylurea, DPP4-inhibitor, metformin + sulfonylurea, metformin +DPP4-inhibitor) according to prior versions of the protocol.
- Patients who were screen failed due to exclusionary HbA1c 7.0% (53 mmol/mol) - 7.4% (57 mmol/mol) at Visit 1 according to prior versions of the protocol. Patients

Proprietary confidential information.

© 2016 Boehringer Ingelheim International GmbH or one or more of its affiliated companies. All rights reserved.

This document may not - in full or in part - be passed on, reproduced, published or otherwise used without prior written permission.

who were screen failed due to exclusionary HbA1c below 7.0% or above 11.0% cannot be re-screened.

- Patients who were screen failed due to exclusionary mean seated DBP (Visit 1) according to prior versions of the protocol. However, mean seated SBP (Visit 1) must have been 140-180 mmHg at the previous screening.
- Patients who were screen failed due to taking 4 antihypertensive medications (≥ 4 weeks prior to randomization) according to prior versions of the protocol.
- Patients who were screen failed due to out-of-window visits prior to ABPM testing (Visit 2.2). If ABPM testing has commenced, no re-screening is permitted.

A patient who was screen failed due to any of the above screen failure reasons is permitted to be re-screened once only. A new patient number should be assigned to the re-screened patient who should be re-consented. Rationale for re-screening must be document in source documents.

Re-screening is not permitted for patients who were screen failed due to other reasons.

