Rescue medication, for the treatment of hypertension, can be initiated during the double-blind treatment period of the trial (i.e. from Visits 3-7.2) and during follow up period but only if the criteria below are met:

- Week 1 – 4 (i.e. up to and including the result from Visit 4.0):
The patient has a mean seated SBP level ≥ 180 mm Hg and/or mean seated DBP level ≥ 110 mm Hg at the clinic visit
- Week 4 – 26 (i.e. from the day after Visit 4.0 onwards):
The patient has a mean seated SBP level ≥ 160 mm Hg and/or mean seated DBP level ≥ 100 mm Hg at the clinic visit

The above results should be confirmed, meaning that there is a minimum of two seated blood pressure measurements (second measurement at the investigational site on a different day to the initial measurement).

If the above criteria are met, the initiation of rescue medication is at the Investigator's discretion, based on the patient's current clinical condition (e.g. ongoing illness etc.). The choice of rescue medication will depend upon the current medication. Adjustment of the current therapy or addition of another antidiabetic and/or antihypertensive medication would be appropriate. Rescue medication and its dosage will be left to the discretion of the Investigator and the administration of rescue medication is to be conducted according to GCP with the exception of the following:

- Due to their known effect on blood pressure, thiazolidinediones (eg pioglitazone) and GLP-1 analogs must not be used as rescue medication for hyperglycemia.
- Any SGLT-2 inhibitor that is or may become available during the conduct of this trial must not be used as rescue medication.

Proprietary confidential information.

© 2016 Boehringer Ingelheim International GmbH or one or more of its affiliated companies. All rights reserved.

This document may not - in full or in part - be passed on, reproduced, published or otherwise used without prior written permission.

Regardless of the choice made, rescue medication should be taken in accordance with the local prescribing information of that respective medication, taking into account potential contraindications. Rescue medication can be used from when it is initiated until the end of the trial.

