Description of change		3. HbA1c of $\geq 7.05\%$ (538 mmol/mol) and $\leq 11.0\%$ (97 mmol/mol) at Visit 1 (screening)
Rationale for change		Adjustment of lower limit for HbA1c to allow for entry of patients with HbA1c between 7.0% and 7.4%.
Section to be changed	3	Synopsis; Main criteria for inclusion and 3.3.2 Inclusion criteria
Description of change		4. Mean seated SBP 140-180 mmHg and DBP 90–110 mmHg at Visit 1 (screening)
Rationale for change		Removed mean seated DBP criteria to allow for entry of patients with isolated systolic hypertension.
Section to be changed	4	Synopsis; Main criteria for inclusion and 3.3.2 Inclusion criteria
Description of change		6. Treatment with stable doses of at least one but no more than 3 4 antihypertensive medication ≥ 4 weeks prior to randomisation.
Rationale for change		Increased number of permitted background antihypertensive medications to permit entry of patients on 4 antihypertensive therapy. Patients with severe hypertension will still be excluded by upper limit for mean seated SBP in inclusion criteria 4.
Section to be	5	Flowchart- Footnote B

Proprietary confidential information.

© 2016 Boehringer Ingelheim International GmbH or one or more of its affiliated companies. All rights reserved.

This document may not - in full or in part - be passed on, reproduced, published or otherwise used without prior written permission.

Number of global amendment changed		3.0
Description of change		Patients will undergo 24-hour ABPM testing. If patients fail the test testing is unsuccessful , this procedure should be repeated.
Rationale for change		Administrative clarification on ABPM testing outcome.
Section to be changed	6	Abbreviations and Entire Document
Description of change		Updated list of abbreviations and corrected text in document accordingly.
Rationale for change		Administrative change.
Section to be changed	7	Entire Document and Section 9.2 Unpublished References
Description of change		
 1. e01838761 c01678844 2. e01838761 c01678844 [REDACTED] BI 10773 Investigator's Brochure BI-10773 in type 2 diabetes mellitus, current version 13. 11 Feb 2016. 3. R09-1164 — Nathan, et al. Medical Management of Hyperglycemia in Type 2 Diabetes: A Consensus Algorithm for the Initiation and Adjustment of Therapy. A consensus statement of the American Diabetes Association and the European Association for the Study of Diabetes. Diabetes Care 39(1)193] (2009).

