4 CHANGES IN THE PLANNED ANALYSIS OF THE STUDY

There have been four amendments to the protocol.

The TSAP is written according to the changes reported in protocol amendment 4 ([1](#)) (c01945509-06, 18 JUL 2016).

The following additional endpoints or modifications to pre-specified endpoints have been defined:

[figure not shown]
[figure not shown]
- Urinary tract infections (UTIs), genital infections (GIs), malignancies and volume depletion have been added as AEs of special interest (AESIs)
- Orthostatic blood pressure test result at week 24

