	D3.01	Background antidiabetic therapy not taken as specified in the protocol	Antidiabetic background therapy dose changed.	PPS
E	Missing data			
	E.01	No baseline HbA _{1c} value	No valid baseline HbA _{1c} value	FAS
F	Incorrect timing			
G	Trial specific violation			
G1	Inclusion criteria violated			
	G1.10	No black/African American or antidiabetic background therapy not as required	Inclusion criterion checked, see individual inclusion criteria	PPS
	G1.11	Blood pressure at screening out of range	Mean seated SBP outside 140-180 mmHg or DBP outside 90-110 mmHg at Visit 1	PPS

Table 6.2: 1 List of important protocol violations (cont.)

PV Category/ Code		Description	(Comments)	Criterion to check for PV	Exclusion from
	G1.12	Use of none or more than 3 antihypertensive medications or use of antihypertensive medications for less than 4 weeks prior to randomization	See inclusion criterion (as specified in the protocol)	I6 ¹ Protocol Version 4 allows 4 antihypertensive treatments, in previous Versions not more than 3 were allowed	PPS
G2	Exclusion criteria violated				
	G2.20	Use of hypertension treatment with oral Minoxidil	See exclusion criteria	E3 ¹	PPS
	G2.21	Blood pressure out of range at placebo run-in confirmed	Mean seated SBP \geq 181 mmHg or mean seated DBP \geq 111 mmHg during placebo run-in visit and confirmed by a 2nd measurement (not on same day) preferably within 1 day	E4 ¹ from Protocol Version 4 onwards SBP criteria only (no DBP criterion)	PPS
	G2.22	Upper arm circumference exceeds cuff size of BP measurement device	Upper arm circumference that exceeds the upper circumference level of the cuff size of either ABPM and/or BP measurement device	E5	PPS
	G2.03	Night shift worker	Night shift workers who routinely sleep during the daytime and/or whose work hours include midnight	E6	PPS

Table 6.2: 1 List of important protocol violations (cont.)

PV Category/ Code		Description	(Comments)	Criterion to check for PV	Exclusion from
	G2.23	Systolic blood pressure difference of >10 mmHg between the arms at screening	See exclusion criteria	E18 (protocol version 1 only)	PPS
G3	Other trial specific violation				
H	Other safety related violations				
H3	Violation of CTP procedure possibly affecting BP measurement				
	H3.01	Incorrect procedure for BP measurement	Not the same arm used for BP measurement for baseline and last value on-treatment	¹	None
	H3.02	Incorrect device used	Incorrect device used for baseline or last value on-treatment	Manual	None

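### Does the SAP drop patients with a screening DBP outside 90–110 mmHg from the per-protocol set although the current protocol admits them?

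*SAP*

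**What the plan says.** SAP Section 6.2, Table 6.2: 1, lists G1.11 among the violated inclusion criteria, with the comment "Mean seated SBP outside 140-180 mmHg or DBP outside 90-110 mmHg at Visit 1" and exclusion from the PPS. Protocol Section 3.3.2, criterion 4, now reads "Mean seated SBP 140-180 mmHg at Visit 1 (screening", with no diastolic limit. Protocol Section 11.3 (Global Amendment 3, which produced Version 4) gives the reason: "Removed mean seated DBP criteria to allow for entry of patients with isolated systolic hypertension". Protocol Section 3.3.5 lets one group of earlier screen failures return: "Patients who were screen failed due to exclusionary mean seated DBP (Visit 1) according to prior versions of the protocol". SAP Section 4 states: "The TSAP is written according to the changes reported in protocol amendment 4". For the run-in blood pressure, row G2.21 of the same SAP table adds in its criterion column "from Protocol Version 4 onwards SBP criteria only (no DBP criterion".

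Row D3.01 carries the comment "Antidiabetic background therapy dose changed" and also leads to PPS exclusion. On rescue, Protocol Section 4.2.1 says "Adjustment of the current therapy or addition of another antidiabetic and/or antihypertensive medication would be appropriate".

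The PPS has one use: a repeat of the primary HbA1c analysis (Protocol Section 7.3.2; SAP Table 6.3: 1, observed cases).

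**The concern.** Read as printed, G1.11 calls a patient a violator for a diastolic value that the protocol has allowed since Version 4. Rows touched by the same amendment carry a version note and G1.11 shows none, so it looks like the one that was overlooked. Patients with isolated systolic hypertension would then leave the PPS, and the supportive analysis would no longer describe the widened population.

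D3.01 looked wrong for another reason. A patient rescued by a higher dose of background therapy would be removed entirely, while one rescued by an added drug would keep the values before rescue. Rescue happens after randomisation and plausibly more often on placebo, so the PPS comparison could be distorted.

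**Working it through.** **1. How the table handles the Version 4 changes.** Four limits changed by Amendment 3 have a row in the table:

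| Row | Superseded limit still printed in description or comment | Entry in the criterion column |
|---|---|---|
| A2.01 | HbA1c kept if within 7.3–11.2% | from Version 4, within 6.8–11.2% |
| G1.12 | more than 3 antihypertensives | Version 4 allows 4 |
| G2.21 | run-in DBP of 111 mmHg or more | from Version 4, systolic criterion only |
| G1.11 | screening DBP outside 90–110 mmHg | column absent from the text |

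In all three rows that can be read in full, the old limit stays in place and the criterion column overrides it. Old wording in the G1.11 comment is therefore what this table's layout would lead one to expect.

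**2. Whether the G1.11 criterion cell was blank or lost.** Rows elsewhere have six cells. Where no criterion is given (C2.01, C4.01, I2.01), the blank cell is kept. On the page with D2.01, D3.01, E.01, G1.10 and G1.11, every row has five cells, although the page header still names the criterion column.

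The codes point the same way. The current protocol has 8 inclusion and 23 exclusion criteria, 31 in all. The readable criterion column refers to all 23 exclusion criteria (E1 to E23) and to six inclusion criteria (I1, I3, I5, I6, I7, I8), so 23 + 6 = 29 are covered. The two left, I2 and I4, belong to G1.10 (race and background therapy) and G1.11 (screening blood pressure), both on the damaged page. The likely explanation is that the column had entries which did not survive extraction.

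**3. Whether the diastolic limit belongs in the table at all.** Before Version 4, criterion 4 required DBP 90–110 mmHg (Protocol Section 11.3). For patients enrolled then, a value outside that range was a real entry violation, so the table needs the limit. A patient enrolled later with SBP 140–180 mmHg has violated no inclusion criterion, which is the group in which the row stands.

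**4. D3.01.** The row falls in the group for mandatory medication that was not taken, and its description concerns background antidiabetic therapy that departs from what the protocol specifies. Section 4.2.1 itself allows adjusting current therapy as rescue, so description and comment together do not clearly cover rescue. Its criterion cell is also on the damaged page. SAP Section 6.6.1 treats an added drug and a background dose change alike as rescue once either lasts at least 7 consecutive days.

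**5. Size, if the literal reading were right.** The plan's own figure comes first: HbA1c difference 0.6%, SD 1.1%, 64 evaluable per arm, two-sided 5%.

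Power = Φ(0.6 / (1.1 × √(2/64)) − 1.96) = Φ(3.086 − 1.96) = 87.0%, in line with the stated figure above 85%.

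The documents give neither the share of patients enrolled under Version 4 or later nor the distribution of screening DBP. With assumed shares of 50–75% and 30–60%, the number removed would be 154 × 0.50 × 0.30 = 23 to 154 × 0.75 × 0.60 = 69. With an assumed 10% to 50% removed from 64 per arm, the same formula gives:

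| Removed | n per arm | Power in the PPS |
|---|---|---|
| 10% | 57.6 | 83.3% |
| 20% | 51.2 | 78.8% |
| 30% | 44.8 | 73.3% |
| 40% | 38.4 | 66.6% |
| 50% | 32.0 | 58.8% |

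These rows show sensitivity to a guess; they do not estimate a loss. No power is claimed for the PPS anywhere in the plan.

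**The case for a change.** The strongest reply is that a pre-specified table should be judged by what it prints. G1.11 prints a diastolic limit without a version note, in an SAP written to Amendment 4. The blinded report planning meeting, which finalises exclusions, is no full answer, because the table is what that meeting works from, and the March 2017 revision does not list Section 6.2 among the changed sections. The first part fails: the cell where a note would stand cannot be seen, and the missing I2 and I4 codes suggest the column had contents. The second part stands, so nothing here relies on the meeting to repair the table.

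On D3.01, the comment has no minimum duration and no exception for rescue, and the observed-cases rule already sets values after rescue to missing. Removing the whole patient as well is then a further step that depends on an event after randomisation. Taken literally, that is true. But a per-protocol set always conditions on such events. This one also excludes for non-compliance (C3.01) and prohibited medication (D2.01). Whether changed background therapy belongs on that list is a choice on which statisticians reasonably differ, and the possible bias is a reason for basing the primary analysis on the FAS, as SAP Section 6.3 does.

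**Conclusion.** The concern does not hold. That G1.11 was left at the old criterion is an inference from a cell missing in the extracted text, and a table broken in that way is not an error in the plan. The old wording in the comment follows the pattern of its three sister rows and is right for patients enrolled before Version 4. D3.01 shows no contradiction once its description is read with its comment; what remains is per-protocol convention.

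No number of wrongly excluded patients can be derived from the documents; 23 to 69 is the product of two assumed shares. Even on the literal reading, the effect would stop at one supportive HbA1c analysis. The primary and the four key secondary tests run on the FAS (SAP Sections 7.4.1 and 7.5.1), and no blood pressure endpoint uses the PPS. The conclusion assumes that the G1.11 criterion cell was lost rather than left without a version note. The layout and the code count support this but cannot prove it.

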6.3 PATIENT SETS ANALYSED

The following analysis sets will be defined for this trial.

- Screened patients set (SCR): All patients screened for the trial, with informed consent given and who completed at least one screening procedure at Visit 1.
- Randomised set (RS): All patients from the SCR who were randomised to trial drug, regardless of whether any trial drug was taken.
- Treated set (TS): All patients who were randomised and treated with at least one dose of trial drug. The TS is the basis for the safety analyses in the double-blind period.
- Full analysis set (FAS): All patients randomised, treated with at least one dose of trial drug, and with a baseline and at least one on-treatment HbA_{1c} value. The FAS is the basis for the primary efficacy analysis.
- Per-protocol set (PPS): All patients in the FAS without iPVs leading to exclusion. See [Table 6.2: 1](#).

No efficacy or safety analyses are planned for the RS. In [Table 6.3: 1](#) the data sets which are to be used for each category class of endpoint are illustrated.

Table 6.3: 1 Summary of which data sets will be used for which class of endpoints

Class of endpoint	TS	FAS	PPS
Primary		OC OC-AD OC-IR LOCF MI	OC
Key secondary - BP endpoints - Other endpoints		OC-AD (not for ABPM endpoints) OC-H OC-IR LOCF-H OC-AD OC OC-IR LOCF	
Subgroup analyses: - BP endpoints - Other endpoints		LOCF-H OC-H OC	
Binary efficacy endpoints - BP endpoints - Other endpoints		NCF-H NCF	
Other continuous efficacy endpoints - BP endpoints - Other endpoints		OC-H LOCF-H OC LOCF OR#	
Safety endpoints	OR LOCF-IR [^] OC-IR [^]		
Disposition	OR		
Demographics		OR	
Baseline efficacy		OC	

[figure not shown]
Note: LOCF=Last observation carried forward; OC=Observed cases; OR=Original result;

[figure not shown]
MI=multiple imputation

[figure not shown]
Further details of the imputation methods can be found in [Section 6.6](#).

[figure not shown]
#OR results will only be presented for time to first rescue medication and number of patients with rescue.

[^] LOCF-IR and OC-IR will only be used for lipids.

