and will be reported. If determined by investigator as necessary for patient safety, new antidiabetic medication regimen can be started immediately after discontinuation and must be recorded in eCRFs.

For the analysis of this trial it is absolutely crucial that all planned assessments are done as planned, even if patients discontinue trial treatment. All patients who discontinue from treatment after randomisation (Visit 3 and beyond) and who do not withdraw consent will be followed up for the intended regular treatment period. All assessments related to the primary and secondary endpoints must be performed as if the patient would have remained on treatment. Details of procedures to be followed for patients prematurely terminating the trial treatment can be found in Section 6.2.3).

If a patient withdraws consent, participation in the study will end, the study medication will be stopped and the study staff will try to arrange tests for end of treatment procedures and a follow-up visit (Visit 8 procedures) with the patient for the patient's safety (For further details please see Section 6.2.3). All used medication kit boxes and remaining study medication should be returned. Patients who withdraw consent will not be contacted any more about the study.

Patients who withdraw or discontinue from the trial after randomisation will not be replaced.

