7.3 PLANNED ANALYSES

The statistical analysis will be based on the following populations.

Treated Set

The treated set will consist of all patients who were randomised and treated with at least one dose of trial medication.

Full Analysis Set

The full analysis set (FAS) will consist of all randomised patients who were treated with at least one dose of study drug and had a baseline and at least one on-treatment HbA1c measurement

Per Protocol Set

The per-protocol set (PPS) will consist of all randomised patients who are part of the FAS but who do not have any important protocol violations (IPV) leading to exclusion. Further details on the definition of the PPS and the definition of IPV's will be provided in the TSAP.

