6 GENERAL ANALYSIS DEFINITIONS

6.1 TREATMENT(S)

There will be 5 treatment study phases in this trial: screening, placebo run-in, study treatment phase (with either empagliflozin, matching placebo), post-treatment and post-study.

Table 6.1: 1 Treatment regimens / study intervals

Label	Interval	Start date	Start time
Screening	Screening period	Date of informed consent	00:00
Run-in	Run-in	Date of first administration of run-in medication	00:00
Placebo Empagliflozin	Double-blind treatment period	Date of first administration of double-blind study medication	Time of first administration of double-blind study medication, 12:00 if missing
Post-treatment	Post-treatment	Date of last intake of trial drug + X* +1 day	00:00
Post-study	Post-study	Last contact date +1 day	00:00

* The endpoint specific follow-up periods for the assignment to active treatment are presented in detail in [Section 6.7](#). This is relevant for the statistical programming team only.

The purpose of the definitions above is to describe all the different study/treatment intervals, in which a patient can be assigned during the course of the trial. Note that the term “treatment regimen” can also cover time periods with no active treatment.

The endpoint-specific follow-up periods for the assignment to active treatment are presented in detail in Section 6.7.

The efficacy analyses will follow the intention-to-treat (ITT) principle in assigning patients to treatment groups, i.e. patients will be analysed as randomised.

Safety analyses will assign patients to the treatment group as treated. If a patient erroneously receives the wrong trial drug, the patient will be analysed as per the first treatment received. Drug-related AEs are analysed according to actual medication taken. Actual medication taken refers to medication at onset of AE. In addition, AEs with an onset during the time of the incorrect study treatment will be listed separately.

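### Patients who stop before any on-treatment HbA1c are in no efficacy analysis, so the drop-out sensitivity analyses omit the earliest drop-outs although the protocol follows them to Week 24

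*SAP*

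**What the plan says.** - **FAS.** SAP 6.3 requires patients to be randomised, "treated with at least one dose of trial drug, and with a baseline and at least one on-treatment" HbA1c value. Protocol 7.3 has the same condition: "had a baseline and at least one on-treatment HbA1c measurement".
- **On-treatment.** Under SAP 6.7 and Table 6.7: 1, an HbA1c counts up to 7 days after the drug stop date. The limit for blood pressure and body weight is 1 day. The first post-baseline window opens on Day 2.
- **Where the analyses run.** In Table 6.3: 1 the FAS column for the primary endpoint reads "OC OC-AD OC-IR LOCF MI", and for the key secondary blood pressure endpoints "OC-AD (not for ABPM endpoints) OC-H OC-IR LOCF-H". Weight, binary, other continuous and subgroup analyses are also on the FAS. The per-protocol set is a subset of it.
- **Other sets.** For the randomised set, "No efficacy or safety analyses are planned for the RS". For the treated set, "The TS is the basis for the safety analyses in the double-blind period".
- **Follow-up after stopping.** Protocol 3.3.4.1 states: "For the analysis of this trial it is absolutely crucial that all planned assessments are done as planned, even if patients discontinue trial treatment". Section 6.2.3 repeats this. It adds a premature treatment discontinuation (PTD) visit with all Visit 7.2 assessments, due within 7 days of the last dose or as soon as possible, and then a return to the visit schedule.
- **ITT.** SAP 6.1 says: "The efficacy analyses will follow the intention-to-treat (ITT) principle in assigning patients to treatment groups". This governs which arm a patient is counted in, not who is analysed.

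**The concern.** The protocol pays for off-treatment follow-up and says that the analysis depends on it. For one group the SAP then has no efficacy analysis that could use the data: patients who stop before the first post-dose HbA1c, have none within 7 days of the last dose, and return later.

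Entry to the FAS is decided after randomisation, by an event that may be related to tolerability. SAP 6.6 says that several methods will be used to assess the impact of missing data. All of them start from a set that has already lost the earliest drop-outs, who are among the most informative patients for that question. A reassuring sensitivity result would then say less than it appears to.

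**Working it through.** **1. The plan's own figures.** Protocol 7.6 assumes an HbA1c difference of 0.6 with SD 1.1, a 24-hour SBP difference of 5 mmHg with SD 10, and a weight difference of 2 kg with SD 2.3, with 64 evaluable patients per arm. A two-sample t-test at two-sided 5% gives 86.5% power for HbA1c (stated >85%), 80.2% for SBP (stated 80%) and 99.8% for weight (stated 99%). 64 × 1.20 = 76.8, rounded up to 77. The figures reproduce, so 0.6, 1.1 and 77 are used below.

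**2. Who is left out.** Let the last dose be on Day L. An HbA1c admits the patient to the FAS if taken from Day 2 to Day L + 7. The flow chart puts Visit 4 on Day 29 with a window of −7/+3 days, so Days 22 to 32.
- An on-schedule Visit 4 counts if L + 7 ≥ 29, that is, L ≥ 22.
- No in-window Visit 4 can count if L + 7 < 22, that is, L < 15. Such a patient needs a PTD visit (or another HbA1c) within 7 days of the last dose.

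Example: last dose on Day 10, PTD visit on Day 25, return at Week 24. The last admissible day is 17. The Day 25 and Week 24 HbA1c values are both post-treatment, and the patient is outside the FAS.

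**3. Which analyses this touches.**
- *Primary OC model and LOCF for HbA1c:* both use on-treatment values only (SAP 6.6.2.2, 6.6.2.4). These patients have none, so a wider set changes nothing.
- *ABPM, LOCF-H:* the first post-baseline recording is Visit 5.1 (Week 11). A patient who stopped before Week 4 has no on-treatment recording to carry forward.
- *Weight (OC) and trough seated SBP (OC-H):* their 1-day limit is tighter than the 7 days for HbA1c, and they are measured at the same visits. A set of their own would add only a patient whose HbA1c sample was missing at the sole on-treatment visit.
- *OC-AD, OC-IR and MI:* their definitions are not in the public text. Table 6.3: 1 nevertheless places them on the FAS, so any off-treatment or imputed values that they would use for these patients are excluded.

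**4. Size, by assumption.** The documents give no count. Suppose k of 77 empagliflozin patients are left out, have no effect off drug, and any excluded placebo patients resemble the rest of their arm. Restoring them gives a difference of 0.6 × (77 − k)/77.

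| k of 77 | HbA1c difference | Change | Power at 77 per arm |
|---|---|---|---|
| 0 | 0.600 | – | 92.0% |
| 2 | 0.584 | 0.016 | 90.6% |
| 4 | 0.569 | 0.031 | 89.0% |
| 8 | 0.538 | 0.062 | 85.4% |

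The standard error of the difference is 1.1 × √(2/77) = 0.177. The change at k = 4 is 0.031/0.177, or about 0.18 of a standard error. At k = 8 it is 0.062/0.177, or about 0.35.

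**The case against.** The group is narrow. A patient must stop before Visit 4, have no HbA1c within 7 days, and still come back. Protocol 6.2.3 makes the follow-up of stoppers conditional on willingness and feasibility, so some will never return. The FAS definition is prespecified and agrees between protocol and SAP, and the confirmatory tests do not depend on these patients. All of this stands, and it limits the point to the sensitivity analyses.

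Four stronger readings are tempting, and the documents do not support them.
- *Early stoppers as a whole are left out.* They are not. Anyone with a Visit 4 HbA1c within the limit, or a timely PTD visit, is in the FAS.
- *The confirmatory blood pressure and weight tests are distorted by a rule about HbA1c.* The third step of the working shows almost no force in this. Nor are the blood pressure values unseen: SAP 7.8 and 7.8.3 summarise vital signs on the treated set, descriptively.
- *The bias always favours the drug.* That needs exclusions on empagliflozin with no benefit, no offset from placebo and no new treatment. Protocol 3.3.4.1 allows new antidiabetic medication straight after discontinuation, which could lower Week 24 HbA1c.
- *24-hour SBP is overstated by 4/77 × 5 = 0.26 mmHg.* No planned analysis corresponds to this, because Table 6.3: 1 does not use OC-AD for ABPM endpoints.

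**Conclusion.** The point holds for patients with no HbA1c from Day 2 to 7 days after the last dose. They are in no efficacy analysis, while the protocol asks for their endpoint assessments to continue to Week 24. Its weight falls on OC-AD, OC-IR and MI, which run on a set selected after randomisation.

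The number lost is probably small. The effect on HbA1c is illustrative only: about 0.03 on 0.6 for 4 of 77 empagliflozin patients with no effect and no placebo exclusions, under a fifth of a standard error. Neither its actual size nor its direction can be taken from the documents. The issue is selection rather than power. What OC-AD, OC-IR and MI contain cannot be judged from the public text; only their placement on the FAS is shown.

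**What to change.** 1. Keep the FAS for the primary OC model and for the confirmatory LOCF-H, OC and OC-H tests.
2. Run the HbA1c sensitivity analyses that use off-treatment or imputed values on all randomised and treated patients with a baseline and any post-baseline HbA1c, on or off treatment. This means MI, and OC-AD as far as its definition includes off-treatment values.
3. For OC-AD of body weight and trough seated SBP, define the set by that endpoint's own baseline and any post-baseline value.
4. Report by arm how many treated patients fall outside the FAS.

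Cost: wording in SAP 6.3 and Table 6.3: 1, and a little extra programming. Under the protocol's procedures the data are already to be collected. The sensitivity estimate may become slightly less favourable.
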